## 1. Study Procedures

The study will enroll for a total of 12 months. Projected enrollment is 32 newly diagnosed patients and previously diagnosed patients not in care. As of May 8, 2017 the Moore clinic HIV practice will be incorporated into a new clinic, the John G. Bartlett Specialty Practice (JGBSP). Throughout the rest of this protocol, activities related to this practice will be referenced as the JGBSP clinic.

### *Patient recruitment*

We will utilize existing HIV linkage to care services for newly and previously diagnosed patients identified at the Johns Hopkins East Baltimore campus, the JGBSP clinic and at the BCHD STD clinics to explore the feasibility and acceptability of RHTI in these settings. All patients identified in the Hopkins ED, Johns Hopkins inpatient HIV service, the JGBSP clinic and BCHD STD clinics who are newly diagnosed with HIV (test positive by 3rd or 4th generation HIV test or detectable HIV viral load with no previously documented positive HIV test by medical record and/or self-report) and patients with previous HIV diagnosis but by self-report are not in care and not on ART (> six months without HIV care and ART) will be referred to the Rapid HIV treatment initiation, Access and Engagement in care (RHAE) Research Assistant (RA) by call or text to a dedicated smart phone. At the time they are identified as needing a referral for HIV treatment services, a brief description of the study will be given to potentially eligible patients and a referral to the RHAE RA will be made with patient permission. In the ED, this referral will be made by ED HIV testing team members and/or ED clinicians. In the JGBSP clinic, the referral will be made by social work staff, nurses and/or medical providers. In the BCHD STD clinics, referrals will be made by patient advocates and/or medical providers. The linkage team will provide linkage services as per usual. In situations when potentially eligible patients present for clinical care when a Project RHAE staff member is not available to accept a referral and/or leave the clinical area before learning about the study, referring providers and staff who engage with the patient for treatment after the initial interaction will present the study and elicit interest and permission for referral at a later date in person or by phone. This may include patients who have been hospitalized at Johns Hopkins Hospital in which case the study team will discuss potential enrollment with the inpatient care team prior to approaching the patient for consent.

### *Patient consent, survey administration*

After referral to the RA, the RA will describe the study to the patient and assess patient eligibility. A study clinician will confirm patient eligibility and the RA will consent patients who wish to enroll. Once consented, the RA will collect contact information and administer a standardized enrollment survey (Table 1). A tablet or computer will be used to record survey responses which will be uploaded to a secure REDCap Database. Domains assessed include illicit drug and alcohol use, depression and panic symptoms, stigma, quality of life, HIV knowledge and social support. The survey will assess anticipated barriers and facilitators to HIV care and adherence to medication and acceptability of RHTI. Date, time and location of HIV clinic follow up will be noted. To ensure adequate ability to obtain follow up information, patients referred to HIV care outside of Johns Hopkins and/or BCHD STD clinics will not be eligible for enrollment.

If the patient is eligible but declines enrollment, he or she will be offered enrollment in the survey-only study of RHTI (IRB00110075). A log of potentially eligible patients

who are not enrolled in the study will be kept by the Project RHAE study staff. This log will be kept in a secure Johns Hopkins network data base and will not include protected health information. The log will include: age, clinical site, whether the patient was newly or previously diagnosed, HIV risk factor, reason patient did not enroll, and if the patient enrolled in the survey-only study. Protected Health Information of patients referred by clinical staff who are not eligible or choose not to consent to enrollment will be destroyed.

*Implementation of RHTI protocol at the Johns Hopkins ED and JGBSP clinic*

Patients recruited from the Johns Hopkins ED and/or JGBSP clinic social work will complete his/her ED/social work visit and will then be seen in the JGBSP clinic by a JGBSP clinic clinician for a medical HIV intake visit and prescription with receipt of ART starter pack. Patients recruited from the BCHD STD clinics will see be seen in the BCHD STD by a clinician for medical intake visit and prescription and receipt of ART starter pack. The clinicians who evaluate patients and initiate treatment will be those who provide continuity HIV care in the clinics. The date and time of the medical visit to initiate treatment at JGBSP clinic and BCHD STD clinic will be as soon as possible and the visit may occur as soon as immediately after recruitment (which is preferable) or may occur on a day other than the day of recruitment if the initial encounter occurs while the clinic is closed, is too late in the day to complete before clinic closes or patient prefers an appointment at a later date. The medical intake will take place no more than one week after consent is obtained. The intake will be as per usual in the JGBSP and BCHD HIV clinics. The following clinical labs will be obtained at the time of enrollment, as part of standard of care: CD4 count, HIV viral load, HIV genotype, CBC, comprehensive metabolic panel, urinalysis, viral hepatitis, syphilis serologies, GC/CT screening based on risk. As part of standard of care, clinicians and/or clinic staff (registered nurse, pharmacist) provide counseling on medication education, potential side effects and adherence. ART prescriptions will be written for at least 14 days of an antiretroviral medication regimen chosen at the discretion of the prescribing provider. Prescriptions for more than 14 days of medication can be prescribed at the discretion of the prescribing provider. Providers in the JGBSP and BCHD HIV clinics have expertise in prescribing antiretroviral medications and caring for HIV-infected patients and they will take into consideration adverse drug-drug interactions with other patient medications and patient comorbidities when choosing the starter pack of antiretroviral medications as per standard of care. Providers will also educate patients about the antiretroviral regimen and dosing recommendations as per standard of care. Pill boxes will be offered with each starter pack. At each clinic, patients are provided with 24/7 clinic contact information should he/she experience adverse side effects to medication and/or experience a medical emergency. Prescribing providers are responsible for reviewing the laboratory results and will follow up with the patient on any regarding any abnormalities requiring urgent/emergent medical attention including need to discontinue antiretroviral medication due to contraindications to a component in the regimen such as estimated creatinine clearance <30 mL/min (a contraindication with tenofovir alafenamide) or due to HIV resistance to a component of the antiretroviral regimen. Medical follow up will be scheduled within two to four weeks.

Medical visits will be documented and billed as part of the patient's medical care. HIV intake, baseline labs and prescription of ART is standard of care for HIV treatment. RHTI accelerates the usual time it takes to receive a medical evaluation for HIV and ART prescription but does not involve investigational medications or procedures. Date of

consent and enrollment in the study will be documented in the medical record by a member of the research team.

For patients who enroll in the study who are admitted to the hospital from the Johns Hopkins ED, research physicians will consult with the inpatient attending to discuss either initiating ART while inpatient, with inpatient ID consultation if admitted to a non-ID service, and/or discharging the patient with a starter pack of ART and close follow up in the JGBSP clinic after hospital discharge (within one week of discharge).

Patients at Johns Hopkins and BCHD will engage in a social work intake as per usual. This intake includes a brief psychosocial and insurance assessment and urgent referrals for psychosocial services and/or initiation of medication and/or insurance coverage as needed. Intake also includes Ryan White eligibility determination. Ryan White eligible patients who are uninsured or need copay assistance at the JGBSP clinic and BCHD STD clinics will receive a Ryan White voucher to cover the full cost or copay of the antiretroviral medication prescription.

Study participants will receive \$25 cash payment for study enrollment. It is estimated the consent process will take about 30 minutes, the survey portion 45 minutes, and the medical intake, phlebotomy, social work intake and receipt of medications will take two hours.

At week four, all patient study participants will be contacted by the RA to repeat questions from the enrollment survey in addition to questions about medication adherence and patient satisfaction with the HIV linkage team (Table 1). Study participants will receive \$50 for completion of the week four survey. HIV linkage and care outcomes data will be extracted from the medical record.

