### 3. Drugs/ Substances/ Devices

Prescriptions for at least fourteen days of the antiretroviral medication regimen chosen by the prescribing provider will be prescribed and dispensed to participants. These FDA-approved drugs will be used according to the FDA-approved indication. Providers in the JGBSP and BCHD HIV clinics have expertise in prescribing antiretroviral medications and caring for HIV-infected patients and they will take into consideration adverse drug-drug interactions with other patient medications and patient comorbidities when choosing the starter pack of antiretroviral medications as per standard of care.

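### Does the 14-day minimum ART supply clash with a follow-up visit at two to four weeks?

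*Protocol*

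**What the plan says.** Section 1 (Study Procedures), where it describes how RHTI is carried out, gives the supply rule: "ART prescriptions will be written for at least 14 days of an antiretroviral medication regimen chosen at the discretion of the prescribing provider". The next sentence removes any ceiling: "Prescriptions for more than 14 days of medication can be prescribed at the discretion of the prescribing provider". Section 3 (Drugs/ Substances/ Devices) repeats the floor: "Prescriptions for at least fourteen days of the antiretroviral medication regimen chosen by the prescribing provider will be prescribed and dispensed to participants".

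The description of the intake visit ends with the follow-up rule: "Medical follow up will be scheduled within two to four weeks". It does not say which day the count starts from. The natural reading is the intake visit, but intake can lag behind consent: "The medical intake will take place no more than one week after consent is obtained".

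The second survey, which adds adherence questions, is also in Section 1: "At week four, all patient study participants will be contacted by the RA to repeat questions from the enrollment survey in addition to questions about" (the sentence then names adherence to treatment). Its starting day is not given either. Table 1 lists the adherence instruments, and a questionnaire on barriers to medication and appointments, at week 4.

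Patients admitted from the ED who go home with a starter pack have their own rule: they are seen in clinic within a week of discharge.

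No text describes refills, and none forbids them.

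**The concern.** Read side by side, the two numbers look mismatched. The minimum supply covers only the first day of a follow-up window that stays open for another two weeks. A patient can be treated exactly to protocol, run out on day 14 and not be seen until day 28. More drug is allowed but not required.

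If that happened often, two things would be at stake. The first is continuity of treatment in the first month. The second is what the week-4 data mean. A patient who took every dose supplied could report many days without drug, and a delivery gap would be read as poor adherence. Time to an undetectable viral load could lengthen for the same reason. In a study of whether rapid initiation is feasible and acceptable, it matters whether a shortfall came from the patient or from the supply.

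**Working it through.** The protocol states no gap or coverage figure, so there is nothing to reproduce. The check is day arithmetic.

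**Inputs**
- Supply S: at least 14 days, no upper limit (Sections 1 and 3).
- Visit day V: 14 to 28 (Section 1), counted from intake unless stated otherwise.
- Lag L from consent to intake: 0 to 7 days (Section 1).
- Survey day: 28, counted from consent or from ART start (Section 1, not specified).

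**Gap before the visit**, assuming no refill: G = max(0, V - S).

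| Supply S | V = 14 | V = 21 | V = 28 |
|---|---|---|---|
| 14 | 0 | 7 | 14 |
| 21 | 0 | 0 | 7 |
| 28 | 0 | 0 | 0 |

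Every cell complies with the protocol. The 14-day gap is one corner of the table. If visits were spread evenly over days 14 to 28 (an assumption with no support in the text) and every patient received the minimum, the mean gap would be 21 - 14 = 7 days.

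If the follow-up window runs from consent and L = 7, the latest visit falls on treatment day 28 - 7 = 21. The largest gap is then 21 - 14 = 7 days.

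**Gap before the week-4 survey**, with minimum supply and no further drug:
- Counted from ART start, or from consent with L = 0: 28 - 14 = 14 days; coverage 14/28 = 50%.
- Counted from consent with L = 7: the survey falls on treatment day 21; gap 21 - 14 = 7 days; coverage 14/21 = 67%.

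**What the worst case needs.** A gap of 14 days and 50% coverage require all of the following: the prescriber chooses the minimum, the visit is booked at the end of the window, no refill is issued in between, and the clock starts at ART start (or intake falls on the day of consent). The documents give no frequency for any of these.

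**Do the passages conflict?** Sections 1 and 3 give the same floor. The floor meets the early end of the window, and the discretion to supply more covers the rest. All three rules can be met together with G = 0, so they are compatible.

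**Reach into the outcomes.** Chart follow-up runs 48 weeks, or 48 × 7 = 336 days. A 14-day lapse is 14/336 = 4.2% of it and need not change whether a patient is still on ART at the end. The listed outcomes are counts and times, with no comparator and no hypothesis test in the text, so a lapse biases no contrast. Splitting week-4 adherence by whether supply reached the visit would divide the 32 patients projected in Section 1. If Section 4's 67% participation is applied to 32 identified, it would divide about 21 (0.67 × 32 = 21.4). Subgroups of that size would support little.

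**The case for a change.** The strongest case for a change is that permission is not protection. The discretion sentence allows a longer supply but does not require it, and for any visit after day 14 continuity rests on an individual choice that the protocol does not visibly record. The outcome lists in Section 4 have no item for days supplied or first refill. With 32 patients, each is 1/32, or about 3%, of the sample, so a few lapses would show in the week-4 adherence summary. The remedy would be cheap: a sentence and a data field.

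Part of this stands. The link is unwritten, the starting day of both counts is unstated, and the arithmetic of the worst case is right.

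The rest is weaker. The prescribers are the clinicians who will go on to provide the patient's HIV care and who, by the protocol's account, have expertise in these drugs. Matching a prescription to an appointment is ordinary practice for them. ART is supplied by normal prescription, paid by insurance or by voucher, and nothing makes a refill wait for the visit. Whether days supplied are extracted cannot be judged, because Appendix 2 is not in the text at hand. How adherence is tabulated belongs to the analysis plan. A lapse that did occur under rapid initiation as delivered would itself be an implementation result, and reporting it would not be an error.

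**Conclusion.** The concern does not call for a change. The supply floor and the follow-up window are compatible, and the protocol does not build in an interruption. It leaves the quantity to the prescriber and so permits a lapse of 0 to 14 days before the visit (at most 7 if the window is counted from consent with a one-week lag). The lapse is zero whenever the supply reaches the appointment. The figure does not carry over to patients discharged from hospital with a starter pack, who are seen within a week.

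This rests on two readings of the text: that prescribers use the discretion they are given, and that refills are available before the visit, since nothing bars them. If another document fixed the supply at exactly 14 days or barred refills before the visit, the two rules would conflict for every visit after day 14, and the clinical team would have to reconcile them. As written, this is a gap that clinicians and analysts fill sensibly, in a descriptive study where no stated conclusion turns on it.

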#### *Electronic medical record data extraction*

HIV linkage and care outcomes will be collected for 48 weeks after enrollment and conducted through chart review of the electronic medical record at each site (Appendix 2). Data will be entered in REDCap Database by RHAE RAs through a tablet.

## **2. Inclusion/Exclusion Criteria**

### *Patient Eligibility*

#### Inclusion Criteria:

- Men and women 18 to 65 years of age
- English speaking
- Patients identified in the Hopkins ED, Hopkins JGBSP clinic or BCHD STD clinics who are newly diagnosed with HIV (test positive by 3rd or 4th generation HIV test or detectable HIV viral load with no previously documented positive HIV test by medical record and/or self-report) and patients with previous HIV diagnosis but by self-report are not in care and not on ART (> six months without HIV care or ART)

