### **RHTI acceptability**

- number of patients offered RHTI, number of patients who accept RHTI
- number of patients who receive RHTI.

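### Do the entry criteria let newly diagnosed patients who already started ART under usual care into a rapid-start study?

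*Protocol*

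**What the plan says.** Protocol Section 2 (Inclusion Criteria) gives two routes into the study. The first is for patients described as "newly diagnosed with HIV (test positive by 3rd or 4th generation HIV test or detectable HIV viral load with no previously documented positive HIV test". The second is for patients with an earlier diagnosis who "by self-report are not in care and not on ART (> six months without HIV care or ART". Only the second route mentions treatment status. The Exclusion Criteria cover pregnancy, capacity to consent, care elsewhere, renal function and inability to consent or take part. None concerns ART already started or an intake already done.

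Section 1 (Patient recruitment) provides for patients who come when no study staff are present, or who leave before hearing of the study. For them, "referring providers and staff who engage with the patient for treatment after the initial interaction" are the people who "will present the study and elicit interest and permission for referral at a later date in person or by phone". In the meantime, "The linkage team will provide linkage services as per usual".

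Section 1 (Implementation of RHTI protocol) then has recruited patients seen for intake, prescription and a starter pack, with one time limit: "The medical intake will take place no more than one week after consent is obtained". The same part says that "RHTI accelerates the usual time it takes to receive a medical evaluation for HIV and ART prescription".

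**The concern.** The two routes are not symmetrical, and the late-referral path seems to turn the asymmetry into a real opening. A newly diagnosed patient missed at first contact could go through usual linkage, have the intake, be prescribed ART, and only then hear of the study from the clinician giving that care. On the words of Section 2 this patient still qualifies. The one-week limit runs forward from consent and says nothing about an intake that came before it.

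At stake is what the feasibility results mean. RHTI is meant to shorten the time to evaluation and prescription. A participant started by usual linkage would count among patients started on ART and might be miscounted as having received RHTI. Time to ART would be zero or negative if measured from consent. Measured from diagnosis, it would be a usual-care interval reported under the rapid pathway. In a study this small, even one such patient is visible in the percentages.

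**Working it through.** **Denominator.** Section 1 projects enrolment of 32 over 12 months. Section 4 (Sample Size and Analysis) expects 32 patients identified in 4 months with 67% participation: 32 × 0.67 = 21.4, so about 21. This does not reproduce 32, and the disagreement is a separate matter. Both denominators are used below.

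**Weight of one patient.** 1/21 = 4.8% and 1/32 = 3.1%. The number already on ART at consent, k, is not in the protocol, so k = 0 to 3 is an assumption.

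**If such patients were miscounted as receiving RHTI.** Suppose all other participants start rapidly. The true RHTI share is (n − k)/n:

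| k | n = 21 | n = 32 |
|---|---|---|
| 0 | 100% | 100% |
| 1 | 95.2% | 96.9% |
| 2 | 90.5% | 93.8% |
| 3 | 85.7% | 90.6% |

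**Effect on the proportion started on ART.** Let p be the start rate among the untreated. The reported rate is [p(n − k) + k]/n, which exceeds p by (1 − p)k/n. With p = 0.80 (assumed):

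- n = 21: k = 1 gives (0.8 × 20 + 1)/21 = 81.0%; k = 3 gives (0.8 × 18 + 3)/21 = 82.9%.
- n = 32: k = 1 gives (0.8 × 31 + 1)/32 = 80.6%; k = 3 gives (0.8 × 29 + 3)/32 = 81.9%.

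The excess is 0.6 to 2.9 points. The standard error of an 80% proportion is √(0.16/21) = 8.7 points or √(0.16/32) = 7.1 points. The protocol states no comparator group and no hypothesis test that this excess could tip.

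**A tempting figure that does not apply.** The longest permitted gap from identification to intake is 365 + 7 = 372 days with 12 months of enrolment, or 121.8 + 7 = 128.8 days with 4 months. It describes a patient whose intake follows consent, hence not the patient at issue. A long time since diagnosis is not a defect in itself either, because the second route enrols people with older diagnoses on purpose.

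**What the rest of the protocol presupposes.**

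- Section 1, Patient recruitment: the study is described to people at the point where they are found to need referral for HIV treatment.
- Section 1, Patient consent: a study clinician confirms eligibility.
- Section 1, Implementation: the order is recruitment, then the visit that starts treatment, with baseline laboratory tests and starter pack.
- Section 3: a regimen is prescribed and dispensed to participants.
- Section 4, Table 1: treatment history is asked only of previously diagnosed patients.
- Section 6: the stated aim is ART at diagnosis, or when a patient is found to be out of care.

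**Can a stray case be seen?** Section 4 counts "number of patients who receive RHTI" as its own item, apart from the count started on ART. The consent date goes into the medical record, and time to ART initiation comes from chart review. Comparing the ART start date with the consent date identifies any patient treated before consent.

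**The case for a change.** The best case for a change is that eligibility belongs in the protocol and cannot be left to an analysis plan. Purpose statements and procedures are not criteria, and the clinician who confirms eligibility has no written ART rule for this group. The late path is the protocol's own: clinic nurses and providers may refer, the same clinic does intakes, and inpatients are named as late referrals. One could answer that by then the index test is itself a previously documented positive. But that would also shut out untreated late referrals until six months had passed, which defeats the late path. One line of text would close the gap.

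The literal gap therefore stands, and a clarifying phrase would do no harm. The step from there to a flawed study does not stand. It needs a clinician to enrol a patient already on ART into a study of starting ART, and then to depart from the written order of recruitment, intake and starter pack. Staff who see a patient for treatment after the first contact need not be giving ART. Counting such a patient as receiving RHTI would be an analyst's error that the separate item does not invite. A cap on time to referral would have a cost, since it could turn away untreated late referrals from a study of 21 to 32. Separate counts and time origins may already be set in Appendix 2 or an analysis plan, neither of which is shown.

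**Conclusion.** No change is needed. Section 2 does not expressly bar a newly diagnosed patient who began ART before consent, but the protocol's procedures leave such a patient nothing to receive under RHTI, and staff and analysts can be expected to fill the gap sensibly. Any effect depends wholly on an undocumented number of patients. It is nil if none is enrolled, and 4.8 or 3.1 points of the RHTI share for each one enrolled and misclassified (n = 21 or 32). For the proportion started on ART it is under 3 points, assuming one to three such patients and an 80% start rate among the rest. The conclusion assumes that the eligibility check is made with the study's purpose in mind and that ART start dates are read against consent dates.
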